9.2.1.2. Self-controlled risk interval design

Individuals must meet all the following criteria to be eligible for inclusion in the SCRI design:

- have received a dose of Pfizer-BioNTech bivalent BA.1 or bivalent BA.4-5 vaccine;
- have not received any COVID-19 vaccine in the three months prior to the dose of bivalent BA.1 or bivalent BA.4-5;

PFIZER CONFIDENTIAL

CT24-WI-GL02-RF02 4.0 Non-Interventional Study Protocol Template For Secondary Data Collection Study

01-Jun-2022

Page 20 of 64

- have experienced the specific AESI during the risk or control interval;
- have full accrual of data used to define the event in both the risk and control interval combined, taking into account the data lag and timing of data extraction;
- have a minimum of 12 months continuous enrollment in the data source at time zero.

[figure not shown]
9.2.2. Exclusion criteria

Individuals who have had a diagnosis of the specific AESI being analysed within one year before time zero (to differentiate the recording of previous events from true new events) and at any time before time zero for diabetes type 1 will be excluded from the cohort and SCRI designs.

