9.2. Setting

9.2.1. Inclusion criteria

9.2.1.1. Cohort design

- Individuals must meet all the following criteria to be eligible for inclusion in the cohort study:
 - have a minimum of 12 months (or from birth if enrolled in the data source at birth) of continuous enrollment in the data source at time zero;
 - have complete information on the matching variables;
 - be in the population targeted by recommendations for vaccination with the bivalent BA.1 or BA.4-5 COVID-19 vaccines, either as a booster, ie, an additional dose several months or longer after the two or three-dose primary vaccine series, as per national or regional recommendations, or as primovaccination, ie, as the first ever COVID-19 vaccine received:
 - if an individual has not received any COVID-19 primovaccination, they will meet this criterion;
 - if an individual has received primovaccination, they will meet the above criterion if they:
 - meet the age threshold or other criteria for additional COVID-19 vaccine doses after primovaccination;
 - do not have any comorbidities or other characteristics for which a short interval between doses is recommended by local vaccination policies and have had prior COVID-19 vaccination at least 11 months before baseline;
 - have comorbidities or other characteristics for which a short interval between doses is recommended by local vaccination policies and have had prior COVID-19 vaccination at least 5 months before baseline.

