9.3.2. Outcomes

The list of AESIs to be analysed as outcomes and the preferred study design are based on those proposed by the EMA -sponsored ACCESS project (vACCine COVID-19 monitoring readinESS) and also, for consistency, those included in the ongoing PASS of the Pfizer BioNTech COVID-19 monovalent vaccine (EUPAS41623). The AESIs are listed in Table 1 by body system, with the corresponding risk interval and preferred study design (Section 9.1). Clinical validation will be considered for specific AESIs.

Table 1. Safety outcomes: adverse events of special interest (AESIs) with estimated risk intervals and preferred study design

Body system / classification	Adverse event of special interest	Estimated risk interval (days)*	Preferred study design*
Autoimmune diseases	Guillain-Barré syndrome ^a	42	Cohort/SCRI
	Acute disseminated encephalomyelitis	42	Cohort/SCRI
	Narcolepsy ^a	42	Cohort/SCRI
	Acute aseptic arthritis	42	Cohort/SCRI
	Diabetes mellitus type 1	365	Cohort
	(Idiopathic) thrombocytopenia ^a	42 ^a	Cohort/SCRI
	Thrombosis thrombocytopenia syndrome (TTS) ^a	15 ^a	Cohort/SCRI
	Myositis	365	Cohort
Cardiovascular system	Acute cardiovascular injury including microangiopathy	365	Cohort
	Arrhythmia	365	Cohort
	Heart failure	365	Cohort
	Stress cardiomyopathy	365	Cohort
	Coronary artery disease	365	Cohort
	Myocarditis or pericarditis ^a	7; 14; 21	Cohort/SCRI
	Myocarditis ^a	7; 14; 21	Cohort/SCRI
	Pericarditis ^a	7; 14; 21	Cohort/SCRI
Circulatory system	Coagulation disorders: thromboembolism, haemorrhage	28	Cohort/SCRI

PFIZER CONFIDENTIAL

CT24-WI-GL02-RF02 4.0 Non-Interventional Study Protocol Template For Secondary Data Collection Study

01-Jun-2022

Page 23 of 64

090177e19fa902a7Approved\Approved On: 12-Jan-2024 21:20 (GMT)

Table 1. Safety outcomes: adverse events of special interest (AESIs) with estimated risk intervals and preferred study design

Body system / classification	Adverse event of special interest	Estimated risk interval (days)*	Preferred study design*
	Single organ cutaneous vasculitis	28	Cohort/SCRI
	Cerebral venous sinus thrombosis	28 ²⁸	Cohort/SCRI
Hepato-gastrointestinal and renal system	Acute liver injury	365	Cohort
	Acute kidney injury	365	Cohort
	Acute pancreatitis	365	Cohort
	Rhabdomyolysis	365	Cohort
	Glomerulonephritis	365	Cohort
Nerves and central nervous system	Generalised convulsion	42	Cohort/SCRI
	Meningoencephalitis	42	Cohort/SCRI
	Transverse myelitis ^a	42	Cohort/SCRI
	Bell's palsy	42	Cohort/SCRI

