 - **EpiChron:** The EpiChron Cohort Study links socio-demographic and clinical anonymised information for all the inhabitants of Aragon region, built from the BIGAN platform. The Aragon BIGAN platform integrates a technical infrastructure and a data lake

gathering individual data from the regional health service information systems, including primary care, specialised care, hospitalisations, ER episodes, drug prescriptions, image diagnosis, laboratory tests, diagnostics, vaccination, medical history and demographics from the users of the public health system of Aragon, about 2 million individuals with historic data, and an active population of 1.3 million individuals.

- SIDIAP:** The Information System for the Improvement of Research in Primary Care (Sistema d’Informació per al Desenvolupament de la Investigació en Atenció Primària’ [SIDIAP]) SIDIAP includes data from 328 primary care centres managed by the Catalan Health Institute in Catalonia, Spain. The database contains pseudo-anonymised records for >8 million people since 2006, with 5.8 million people active in June 2021 (75% of the Catalan population). SIDIAP is representative of the general population living in Catalonia in terms of age, sex and geographic distribution ³⁴. SIDIAP includes data on the clinical and referral events registered by primary health care professionals and administrative staff in EHRs, demographic information, community pharmacy invoicing data, specialist referrals, and primary care laboratory test results. SIDIAP data can be linked to other data sources and registers at the local and national level.
- UK: Clinical Practice Research Datalink (CPRD)**

 - CPRD includes data from EHRs of general practitioners in the UK who act as gatekeepers for health care and maintains individuals’ life-long EHRs. Secondary care teams also provide information to general practitioners about their patients, including key diagnoses and procedures. The data recorded in the CPRD include demographic information, prescription details, clinical events, preventive care, specialist referrals, hospital admissions, and major outcomes, including death. Currently, CPRD Aurum contains data for approximately 13.3 million individuals [Current acceptable individuals (ie, registered at practices currently contributing data, excluding transferred out and deceased individuals)].

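### The one-year look-back in section 9.2.2 can let long-standing heart failure, coronary artery disease and, in part, narcolepsy count as new events and bias the risk ratio

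*Protocol*

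**What the plan says.** Section 9.2.2 of the protocol excludes "Individuals who have had a diagnosis of the specific AESI being analysed within one year before time zero", with the stated purpose "to differentiate the recording of previous events from true new events". There is one exception: "and at any time before time zero for diabetes type 1 will be excluded from the cohort and SCRI designs".

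Table 1 in section 9.3.2 lists "Heart failure" and "Coronary artery disease" as cohort outcomes with a 365-day risk interval. Neither carries footnote a, which marks the outcomes to be clinically validated. Narcolepsy has a 42-day interval, is analysed in both designs, and does carry that footnote.

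The protocol also treats the two cardiac conditions as pre-existing disease. Heart failure is a frailty surrogate in section 9.3.3.9, and both conditions appear among the at-risk conditions in Table 2.

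On available history, section 9.2.1.1 requires people to "have a minimum of 12 months (or from birth if enrolled in the data source at birth) of continuous enrollment" at time zero, so 12 months is a minimum. Section 9.4 says of SIDIAP: "The database contains pseudo-anonymised records for >8 million people since 2006". It describes CPRD practices as keeping life-long records.

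**The concern.** By using any prior record for type 1 diabetes, the protocol accepts that one year is too short for a disease that does not go away. It does not say why the same reasoning stops there. A person with established heart failure who went a year without a qualifying code is classed as free of the disease at time zero, and a later code can then enter the numerator as a new event.

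Nothing later in the protocol takes such records out for heart failure or coronary artery disease. Matching (section 9.1.1.3) uses only the number of CDC risk conditions. Propensity-score weighting (section 9.7.1.6) can balance old disease between the groups but leaves it in the numerator. Section 9.9 acknowledges reliance on codes and algorithms in general, but not this problem.

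The risk ratio is one of the two reported effect measures. In a safety study, a ratio pulled toward 1 can hide a real increase, and a ratio moved by unequal re-coding can suggest an increase or a protection that does not exist.

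**Working it through.** **1. The plan's own figures.** The protocol gives no number for the look-back. Its only quantitative statement on the risk ratio is Table 3, so I checked that first.

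Limits = exp{ln RR ± 1.96 × √(1/(n·p1) − 1/n + 1/(n·p0) − 1/n)}.

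For n = 1,000,000 per group, p0 = 1 per 50,000 and RR = 2, there are 40 and 20 expected events. The standard error is √(1/40 + 1/20) ≈ 0.274 and the limits are 1.17 to 3.42, as printed. All 27 rows reproduce, within 0.01 or, for the very large upper limits, 0.1%. Table 3 is not in question and serves as the baseline.

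**2. Formulas.** Let I be the true comparator risk in the window, P the risk of a re-recorded old diagnosis in the comparator group, and f = P/(I + P).

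- Equal carry-over: observed RR = (RR·I + P)/(I + P) = 1 + (RR − 1)(1 − f). The risk difference stays at I(RR − 1).
- Exposed group with k times the carry-over: observed RR = RR(1 − f) + k·f.
- P = prevalence × share with no code in the prior year × probability of a qualifying code in the window.

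**3. Heart failure in older people.** All inputs are assumptions: incidence 2% per year, prevalence 8% to 10%, 10% to 20% uncoded, 30% to 50% re-coded within the year, true RR 1.5.

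| | Low | High |
|---|---|---|
| P | 8% × 10% × 30% = 0.24% | 10% × 20% × 50% = 1.0% |
| f | 0.24/2.24 = 11% | 1.0/3.0 = 33% |
| Observed RR | (3.0 + 0.24)/2.24 = 1.45 | (3.0 + 1.0)/3.0 = 1.33 |
| Risk difference | 3.24% − 2.24% = 1.0 point | 4.0% − 3.0% = 1.0 point |

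The true risk difference is also 3.0% − 2.0% = 1.0 point. Its variance is proportional to the sum of p(1 − p) over the groups. Treating the groups as independent, that sum rises from 0.0487 to 0.0533 (low) or 0.0675 (high), so the standard error grows by about 5% to 18%.

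**4. Narcolepsy before any validation.** Assumed: incidence 1 and prevalence 30 per 100,000, 10% to 30% uncoded, 5% to 10% re-coded within 42 days. I = 1 × 42/365 = 0.115 and P = 0.15 to 0.9 per 100,000. A true RR of 5 reads (0.575 + 0.15)/0.265 = 2.7 down to (0.575 + 0.9)/1.015 = 1.5.

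**5. Effect on a Table 3 row.** Same n and true risk as in step 1, true RR 2, f assumed:

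| f | Observed RR | 95% limits |
|---|---|---|
| 0 | 2.00 | 1.17 to 3.42 |
| 10% | 1.90 | 1.14 to 3.18 |
| 25% | 1.75 | 1.09 to 2.82 |
| 50% | 1.50 | 1.01 to 2.24 |
| 75% | 1.25 | 0.93 to 1.68 |

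**6. Unequal carry-over.** At true RR 1 and f = 50%, k = 0.8 gives 0.50 + 0.40 = 0.90, and k = 2 gives 0.50 + 1.00 = 1.50. At true RR 2, k = 2 gives no bias (1.00 + 1.00 = 2.00).

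**The case against.** Much of the case against is sound and limits the point.

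- **Narcolepsy is protected in part.** It is marked for validation, the abstract plans record review by clinicians blinded to exposure, and section 9.9 says dates of occurrence will be checked for some outcomes. That check can expose an old diagnosis. It is incomplete, because section 9.9 says its extent may be limited and section 9.6 speaks of a sample of events. A reader might take 2.7 to 1.5 as the expected result for narcolepsy. It is a figure for no validation at all.
- **A later code is not automatically an event.** Section 9.6 describes algorithms built from codes, keywords and other concepts such as medications, usually one broad and one narrow. They are not shown, so only codes that meet the algorithm matter.
- **The direction is not fixed.** Dilution needs roughly equal carry-over, and the risk difference is then unchanged. A reader might also infer a false excess from more health care contact among vaccinees. The documents give weak support for that: the weighting covariates include health care use, cardiovascular disease and heart failure, and a sensitivity analysis in section 9.7.1.11 excludes people with recent contact.
- **Not every Table 1 outcome is lifelong.** A reader might extend the argument to arrhythmia, glomerulonephritis or myositis as equally permanent. The protocol offers no basis for that. For conditions that recur, an episode after a code-free year may be a real safety event that an any-time exclusion would discard.

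What remains is the gap for heart failure and coronary artery disease. Balancing old disease between groups does not remove it from the event count, and no validation is planned for either.

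**Conclusion.** The point holds in this limited form. The one-year rule does not fully serve its own stated purpose for chronic outcomes. The gap is clearest for heart failure and coronary artery disease, and partial for narcolepsy. It is a fixed eligibility rule in the protocol, not a detail left open for the analysis plan.

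With equal carry-over and the assumed heart failure inputs, a true risk ratio of 1.5 reads 1.45 to 1.33. The low end is minor and the high end loses a third of the excess. The risk difference keeps its value and loses some precision. With unequal carry-over the bias can go in either direction or cancel. These sizes rest wholly on assumed prevalence, coding gaps and re-coding rates, and the true share of old disease cannot be derived from the protocol.

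The documents do not support the stronger reading that the rule necessarily dilutes every chronic outcome. For acute outcomes one year is a defensible choice.

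**What to change.** - **Section 9.2.2:** extend the any-time exclusion now used for type 1 diabetes to narcolepsy and heart failure, applied to all history available in the data source.
- **Coronary artery disease and other outcomes that can recur as new episodes:** keep the one-year rule in the main analysis. Add to section 9.7.1.11 a sensitivity analysis that excludes anyone with a prior diagnosis in all available history.
- **Acute outcomes:** no change.

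The programming cost is small, since type 1 diabetes already needs the same look-back and 12 months is only the minimum history.

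There are two real costs. Look-back length will differ between individuals: enrolment length is not a matching variable, and matching on residence or practice does not guarantee similar history within a pair. Describing available history by exposure group would show whether this matters. Also, some people with prior disease leave those analyses, so a worsening of established heart failure would no longer be counted under that outcome.

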9.1.1.3. Matching process

As in prior applications of observational studies of the Pfizer-BioNTech COVID-19 using an unexposed comparator,²¹⁻²⁴ the cohort study will match exposed to unexposed individuals using a 1:1 ratio. Matching will be done with replacement, as follows.

- On the day an exposed individual receives a bivalent vaccine dose, individuals will be matched to unexposed individuals who, on that same day, have exactly the same values for the matching variables, provided that both members of the pair meet the eligibility criteria that day. If more than one unexposed individual is found to match a bivalent vaccinated individual, one will be selected at random.
- Exposed individuals will be allowed to have served as unexposed controls in prior matches, and unvaccinated individuals will be allowed to serve as controls more than once (during different time periods).

Individuals will be matched on the following variables, that have been shown to control for confounding well in prior studies:^{21,22}

- Age – 2-year age groups (consecutive years);
- Sex (male, female) – exact matching;
- Place of residence – exact matching, at the level of clinical practice, neighbourhood, or proxy as available (specific for data source);
- History of COVID-19 vaccination, containing the following categories – exact matching:
 - Never vaccinated;
 - Vaccinated with a total of i doses (where i can range from 1 to the maximum number of plausible doses at the time the matching is performed) with the last dose received in calendar month j (where j can range from the first month to the last month of the study period);
- Brand of last COVID-19 vaccine received;
- History of hospitalisation for COVID-19;
- Pregnancy status yes, no (exact matching):
 - Among pregnant women, matching will take a ‘greedy matching’ approach, in which a matched individual will be sought first by last menstrual period (LMP) within 7 days of each other; if no matches are found, the matching period will be extended to 30 days;
- Immunocompromised (yes/no) – exact matching;
- Number of pre-existing conditions considered by the Centers for Disease Control and Prevention (CDC) as risk criteria (0, 1, >1);²²
- Socioeconomic status/education level (as available, exact matching);
- This selection of matching variables is based on prior observational studies.^{22,24,25} The selection of variables will be tailored based on the availability of variables in each data source.

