9.3.3.7. Healthcare utilisation

- Healthcare utilisation in the year and in the 2 weeks before time zero:
 - Number of hospitalisations;
 - Number of emergency department visits;
 - Primary care utilisation;
 - Cancer screening;
 - Other preventive health services, as appropriate
 - COVID-19 tests.

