9.7.1.11. Sensitivity analysis

One sensitivity analysis will estimate the direct effect of vaccination on the AESIs by repeating the main analyses and additionally censoring in the event of a documented SARS-CoV-2 infection. Another sensitivity analysis will exclude individuals who have had contact with the health care system in the 7 days before time zero. Contact with the health care system serves as an indicator of a health event not related to subsequent vaccination that could reduce the probability of receiving the vaccine.²²

If the homogeneity of the data allows, additional sensitivity analyses will be done to estimate the combined pooled effect across data sources.

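### People already in hospital at time zero can be drawn as unexposed controls in the main cohort analysis, which pulls risk ratios down, mainly over short windows

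*Protocol*

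**What the plan says.** Cohort inclusion (Section 9.2.1.1) asks for 12 months of enrolment, membership of the population targeted for vaccination, and that people "have complete information on the matching variables". The sole exclusion (Section 9.2.2) removes "Individuals who have had a diagnosis of the specific AESI being analysed within one year before time zero", extended to any earlier time for type 1 diabetes.

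Under Section 9.1.1.3, "the cohort study will match exposed to unexposed individuals using a 1:1 ratio". Controls are drawn on the day of the vaccinee's dose, "provided that both members of the pair meet the eligibility criteria that day". The only hospital-related matching variable is "History of hospitalisation for COVID-19". Current or recent admission for any cause is not matched.

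Section 9.7.1.11 states: "Another sensitivity analysis will exclude individuals who have had contact with the health care system in the 7 days before time zero". Its reason is that such contact signals a "health event not related to subsequent vaccination that could reduce the probability of receiving the vaccine". The restriction is not part of the main analysis.

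Section 9.3.3.7 lists "Healthcare utilisation in the year and in the 2 weeks before time zero", including the number of hospitalisations, among covariates that may be used as available. Section 9.7.1.6 says that propensity score weights will be used and leaves variable selection and weight construction to the SAP. The abstract makes propensity score methods conditional on need.

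**The concern.** Time zero for the vaccinee is a day on which that person was well enough to be vaccinated. Time zero for the control is the same calendar date, with no matching requirement. Someone in hospital that day for surgery, sepsis or cancer is less likely to be vaccinated, so such people are over-represented among the unexposed. They also have a higher short-term risk of acute events such as thromboembolism, haemorrhage, arrhythmia, acute kidney injury, convulsion and death.

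This raises the control risk and lowers the risk ratio. The primary objective asks whether risk is increased, so the error runs in the unsafe direction. The same-AESI exclusion does not address it, because the inpatients in question were admitted for something else. Matching on age, immunocompromise and number of risk conditions removes part of the difference, but not the part due to the acute illness.

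**Working it through.** **The plan's own precision figure.** Table 3 gives, for n = 100,000 per group, unvaccinated risk 1 per 5000 and RR 2, a 95% CI of 1.17 to 3.42. Expected cases are 40 exposed and 20 unexposed. SE(log RR) = √(1/40 + 1/20 − 2/100,000) = 0.274, and 2 × exp(±1.96 × 0.274) gives 1.17 to 3.42. The other rows of Table 3 reproduce in the same way, so the table contains no arithmetic error.

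**Bias formula.** Let p be the share of controls in hospital at time zero and k their AESI risk over the window relative to other controls. Take the inpatient share among the exposed as 0. Control risk is multiplied by 1 + p(k − 1), so observed RR = true RR / [1 + p(k − 1)]. The documents give neither p nor k. Both are assumptions, and every figure below is before any weighting.

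**True RR of 1, excess lasting the whole window:**

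| p | k = 10 | k = 50 |
|---|---|---|
| 0.2% | 1/1.018 = 0.98 | 1/1.098 = 0.91 |
| 0.5% | 1/1.045 = 0.96 | 1/1.245 = 0.80 |
| 1% | 1/1.090 = 0.92 | 1/1.490 = 0.67 |

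**Against Table 3** (n = 100,000, risk 1 per 5000, true RR 2). With p = 0.5% and k = 50, unexposed cases rise to 20 × 1.245 = 24.9 and the RR reads 2/1.245 = 1.61 (95% CI 0.97 to 2.65). With p = 0.1% and k = 10 it reads 1.98 (1.16 to 3.38). The lower limit falls below 1 only once p(k − 1) exceeds about 0.21. At n = 1,000,000 and the same risk, the threshold is about 0.73.

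**365-day windows.** Table 1 gives 365 days for arrhythmia, acute kidney injury, acute liver injury and death. Suppose the excess is 50-fold for 30 days and absent afterwards. The average is k = (30 × 50 + 335 × 1)/365 = 5.03. A true RR of 1 then reads 1/(1 + 0.005 × 4.03) = 0.98 at p = 0.5%, and 1/(1 + 0.01 × 4.03) = 0.96 at p = 1%. Section 9.7.1.4 also plans estimates at different time intervals for long-follow-up outcomes. At the early intervals the dilution is smaller.

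**What the listed covariates can see.** A patient admitted three weeks before time zero and still in hospital is counted in the one-year number of hospitalisations. If counting is by admission date, the two-week number misses that patient. In the one-year number the patient looks the same as someone discharged long ago. Neither count is an indicator of being in hospital that day.

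**The case against.** The plan has several safeguards. The 7-day contact exclusion is prespecified. Standardised differences are checked before and after weighting (Section 9.7.1.2). Early COVID-19 outcomes serve as a negative control (Section 9.7.1.6). The same-AESI exclusion removes a control whose event was diagnosed earlier in the current stay. Coagulation disorders and generalised convulsion, with 28- and 42-day windows, also have a self-controlled analysis, which uses no unexposed controls.

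These points limit the size of the problem but do not close the gap. The negative control and balance checks can reveal an imbalance without removing it. The sensitivity analysis leaves the main estimate as it is. Arrhythmia, acute kidney and liver injury and death have no self-controlled analysis.

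Three stronger readings are tempting, and the documents do not support them:

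- *That inpatient controls conceal a vaccine risk.* This needs a high inpatient share and a high relative risk together. Neither figure is given, and at the low end of the assumed range the bias is about 2%.
- *That weighting cannot repair the bias.* Section 9.9 says the cohort analysis estimates the effect in the vaccinated. Weights of the form PS/(1 − PS) would bring controls with a very low vaccination probability close to zero weight, provided the model contains a variable that identifies them. Ordinary inverse probability weights would do less. The choice is left to the SAP, which is not at hand.
- *That inpatients have almost no chance of vaccination.* Section 9.7.1.11 says only that a health event could lower it.

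On feasibility, several sources are described mainly as primary care with hospital data by linkage, and the protocol does not say that discharge dates are available.

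**Conclusion.** The design gap stands. Current inpatients are eligible controls in the main cohort analysis, and the protocol names the mechanism but acts on it only in a sensitivity analysis. The expected direction is a risk ratio that is too low.

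The size rests on assumed values. For short windows and early time points, a true RR of 1 reads between 0.98 and 0.67 for shares of 0.2% to 1% and a 10- to 50-fold risk. For 365-day windows a few percent is more likely (0.98 to 0.96 under the 30-day assumption). These figures assume no inpatients among the exposed and no weighting. Weighting may shrink them, and the self-controlled analyses are not affected. The change is worth making because it is cheap and removes a bias against detecting harm, not because a lost signal has been demonstrated.

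**What to change.** Add to Section 9.2.2, for the cohort design and both arms, an exclusion applied before matching: anyone who is an inpatient at time zero (admission on or before that date, discharge on or after it), in data sources that hold admission and discharge dates. Applying it before matching keeps pairs intact. Report which sources could apply it, and keep the 7-day contact exclusion as the wider sensitivity analysis.

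One detail needs settling. Follow-up counts the day of vaccination, and anaphylaxis has a one-day interval. A vaccinee admitted that same day may be the very case the study seeks, and must not be removed by the new rule. If the time of admission is unknown, limiting the rule to admissions dated before time zero avoids this, at the price of keeping controls admitted that day.

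The cost is one eligibility line and its programming. People vaccinated during an admission are no longer represented. Sources without hospital data cannot apply the rule, which adds a difference between sources to the meta-analysis. Reporting where it was applied makes that visible.
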